[IR-1] Data required for primary analyses will be inspected, cleaned, and locked before primary analysis is begun. Data checks will include examination of descriptive statistics for plausibility (e.g. plausible participant age, scale values fall within scale options given), distribution, and missingness. Values with errors will be replaced as missing or, if a correction is verifiable through review of an individual's record, replaced with the correct value in the dataset in Stata 14. For the primary analyses, individual record reviews will be performed for any participants with circumstances in which the primary outcome of contraceptive continuation may be complicated. These include all participants who selected DMPA (The Shot or "Depo") as their main or bridge method choice; participants who stopped their method before their 4-month survey and restarted it again before their 7-month survey; participants who transitioned from use of their bridge method to use of their main method for birth control during the course of the study; participants who became pregnant during the course of the study, after their day of enrollment; participants who were not reached to complete a 4-month survey, but did complete a 7-month survey; and participants with partially complete survey records at 4 or 7 months [IR-4]. Participants who are negative for the primary outcome (i.e. discontinuous) at the time of their 4-month survey will be considered negative for the primary outcome at 7 months, regardless of whether they completed a 7-month survey or not. Baseline outcomes will also be examined for individuals who accidentally completed multiple surveys at baseline, with priority given to the first survey completed. Reliability of scales will be assessed using Cronbach's alpha, as well checks for predictive and discriminant validity. [IR-4]. Reliability of scales will be assessed using Cronbach's alpha, as well checks for predictive and discriminant validity.

Specific Aim 1:

We will assess imbalance by treatment assignment using cross-tabulations and comparisons of within group means and medians. Inference for balance on provider covariates will use chi-squared, Fisher's exact, t, and Wilcoxon tests as appropriate, while differences in patient characteristics will be assessed using mixed effects models with fixed effects for clinic and random effects for provider. [IR-3] Primary analyses of treatment effects will be intention-to-treat, according to treatment assignment, and without regard to use of the tool or seeing an intervention provider. Treatment effects will be estimated using mixed effects linear, logistic, proportional odds, and multinomial models, with fixed effects for clinic and random effects for provider.

Missing data. [MD-1] Missing data will have been minimized by active follow-up of participants. [MD-4] Missing data rates for primary and secondary outcomes as well as important covariates will be reported, in combination with summaries of the reasons for missingness, including dropout and pregnancy. [MD-2] All analyses will handle missing data using 20-fold multiple imputation of missing outcomes, based on iterative chained equations. [MD-3] Summary effect estimates, averaged over the 20 imputed datasets, as well as confidence intervals and p-values, will be calculated using standard methods that account for imputation error.

Sensitivity analyses. [MD-5] Because informative missingness would violate the covariate-dependent missing at random (CDMAR) assumption of the standard multiple imputation procedure, we will conduct sensitivity analyses in which we multiply impute missing data under plausible informative missing data mechanisms – in particular, lower contraceptive continuation rates among participants with missing values of this outcome, in one or both arms. [DR-3] In addition, we will conduct sensitivity analyses controlling for any imbalanced pre-randomization characteristics (e.g., age and parity) that predict outcomes, using 5% changes in the coefficient for the intervention as the criterion for covariate inclusion in the adjusted model. To characterize the influence of individual providers, we will estimate best linear unbiased predictions of the provider effects, and also fit models with additional random provider-intervention interactions, to capture heterogeneity in the effects of the intervention. In all analyses, we will transform continuous outcomes as necessary to meet the normality assumption, model departures from linearity in the influence of continuous covariates, check for influential points, and identify potentially important interactions.

Heterogeneity of treatment effects. [HT-1] We will assess modification of the effect of assignment to the intervention by the following 5 pre-specified factors: age, race/ethnicity, language, parental education, and clinic. We will assess evidence for effect modification by adding the effect modifier and its interaction with the treatment assignment indicator to the primary analysis models specified above. To limit inflation of the type-I error rate, we will only estimate within-stratum treatment effects if the interaction is statistically significant at a Bonferroni-corrected $P = 0.01$, and will cautiously interpret findings. These analyses will use multiply imputed data and corresponding inference methods.

Specific Aim 2: For this aim, we will be assessing the effect of the intervention on counseling at the cluster (i.e., provider) level. We will use Dedoose software to analyze the audio recordings using modified grounded theory, with the coding performed by [name], [name], and [name], with input from patient stakeholder representatives. This coding will focus on the presence or absence of shared decision making and patient engagement in the decision making process. In conducting this coding, we will use concepts drawn from observational measures of shared decision making, including the OPTION scale and the Four Habits Coding Scheme, as well as insight into the counseling process gained through our previous observational study, to identify our initial thematic structure. We will perform iterative coding, with discussions between coders, the PI, and patient stakeholders to clarify concepts and resolve ambiguities. We will then, again in collaboration with stakeholders, qualitatively explore the extent to which the providers altered their behaviors following implementation of the intervention using memo writing, and ultimately compiling these into results.

Specific Aim 3: In order to determine the effect of the intervention on the experience of providing family planning care at the level of both the clinic and the provider, we will perform both qualitative and quantitative analyses. Quantitative analyses, including comparing consultation time and total clinic visit time for patients in the intervention and control group, will use similar methods to those described in Aim 1. We will also compare scores on each sub-scale of the Maslach Burnout Inventory (emotional exhaustion, depersonalization, and personal accomplishment), controlling for baseline values, between providers randomized to the intervention and those randomized to the control group in both bivariate

Last updated November 22, 2016

and multivariate analyses, again controlling for clustering by clinic. In addition, we will conduct a sensitivity analysis controlling for any imbalanced pre-randomization characteristics (e.g., age) that predict outcomes, using changes in the coefficient for the intervention as the criterion for covariate inclusion in the adjusted model. Thematic analysis of interview and focus group transcripts and recordings will again be performed using Dedoose software, using an iterative and collaborative process of coding as described in Aim 2.

Additional Analyses

Intervention arm patient participants' decision support tool data will be analyzed. Participant data input to the tool includes patient preferences around birth control characteristics, their recommended methods, and any questions for their provider.

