- After the visit, each patient will complete a post-visit survey assessing their demographics, their contraceptive methods choice and their opinion of the counseling they received. If the patient must leave the clinic without completing her post-visit survey due to time constraints (and not because she wishes to withdraw from the study), study personnel will attempt to contact the patient using the contact information given at the time of the visit and have them complete the post-visit survey by phone or email. If the patient does not complete the post-visit survey within 48 hours of their initial visit, study personnel will continue to attempt to have them complete the post 48-hours version of the post-survey (in which the time-sensitive questions have been omitted) up to one month after the initial visit.
- Study staff will provide each patient with a flyer summarizing the timing of follow-up and with contact information for study staff in case participant changes her contact information or wishes to dis-enroll.

1. Patient Follow-Up Survey

Each patient will be contacted by whatever method they prefer (phone, mail, SMS, email) at four and seven months after the visit to complete a follow-up survey to assess whether they have continued their contraceptive method. The survey can be completed either over the phone with an RA or on the patient's own time online using REDCap.

- Patient contact information and enrollment dates will be entered into REDCap, where follow-up contact due dates will be calculated. RAs and volunteers will conduct follow-up attempts via the patient's preferred method, logging each attempt and its outcome in REDCap.
- In order to accurately assess whether Depo users got their next shot on time, 4 month follow up calls will begin at 112 days (16 weeks) and 7 month follow up calls will begin at 217 days (31 weeks).
- The secure UCSF email address [contact] has been created and added to each RA's email account to facilitate participant follow-up by multiple people.

Study Protocol

Patient Centered Support for Contraceptive Decision-Making: A Cluster Randomized Controlled Trial of a Contraceptive Decision-Support Tool

November 22, 2016

- Google Voice will be used for text and phone follow-up contact attempts. Contact information will be deleted from the program monthly.

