- Contact attempts for the 4- and 7-month follow-up surveys will be declared unsuccessful after 4 weeks, but participants with unsuccessful contact at 4 months will still have contact attempts made at 7 months.
- Gift cards for completed surveys will be mailed, or can be picked up at the research offices at San Francisco General Hospital if the patient prefers. For more detail on participant reimbursements, see Section V.

2. Patient Disenrollment Procedure

Patients who no longer wish to participate will be withdrawn by the following protocol.

Paperwork

1. *If a participant disenrolls at baseline:* move any study participant consents and/or HIPAA forms) to the folder labeled “withdrawn patients,” stratified by clinic. Shred any contact information forms. Mark on any remaining paperwork the step that the participant was at when they disenrolled, e.g. Mark on consent that the participant disenrolled before completing the HIPAA form. *If a participant disenrolls at any point after baseline* (e.g. at 4 month follow-up), their consent and HIPAA forms should remain in the folder with the rest of the remaining enrolled participants. Shred contact information forms. The following procedure for electronic records should be followed for all participants regardless of when they disenroll from the study.

Electronic records

1. Mark “Yes” for “Dis-enrolled?” and complete reason for disenrollment in tracking sheet.
2. Mark participant as “dis-enrolled” in backend survey of REDCap.
3. Remove follow up dates from the calendar in REDCap.
4. Delete contact information if it was already entered in REDCap, including participant’s first name.

3. Blinding

Blinding of participants and study personnel at baseline was not feasible due to the nature of the intervention. At follow-up, study personnel conducting surveys by phone were not informed of study arm. Consent forms intentionally do not disclose the specific outcomes of interest (i.e., contraceptive continuation), so as not to influence participant behavior. Additionally, participants will not be aware of their arm assignment until after they have been consented. Study staff will be blinded during quantitative data analysis of provider and patient participant data and time study data. However, blinding will not be feasible during qualitative analysis of visits as the presence or absence of the

Study Protocol

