 - Continuation of the chosen method seven months after her visit, without a gap of four consecutive weeks or more. If participants completed a 4 month follow-up survey, they must have started their chosen method by the date of that survey to be considered continuous users. If they did not complete a 4-month follow-up survey and only completed a 7-month follow-up survey, they must have started their chosen method by 20 weeks post-enrollment (4 weeks after their 4-month follow-up milestone). Participants must be currently using their chosen method at the time of the 4-month follow-up survey to be considered continuous users, UNLESS they report this non-use as

part of a <4week gap at the time of the 7 month survey. Participants must be currently using their chosen method at the time of the 7-month follow-up survey to be considered continuous users.

- *Definition of continuation variable:* We will evaluate continuation based on the day of 7-month survey completion, within a 4-week window beginning 7 months after enrollment
- *Definition of chosen method:* In the primary analysis, continued use of any IUD among those choosing either IUD will be classified as continued use of the chosen method; we will conduct an additional sensitivity analysis in which only continued use of the type of IUD originally chosen will be classified as continuous.
- *Treatment of bridge method users:* For primary analysis, any combination of continuous bridge method use with or without subsequent use of the chosen method will be considered continuous; we will conduct a sensitivity analysis in which participants who never start their primary OR start their primary method after the 4-month follow-up survey are not considered continuous users of their chosen method.
- *Treatment of women who become pregnant.* Continuation at 7 months will be multiply imputed for participants who report a pregnancy before this point who had started their chosen method before 4 months and were continuing to use it at the time they became pregnant. Participants reporting discontinuation prior to pregnancy will be counted as non-continuers.
- *Continuous users of coitally-dependent methods:* For primary analysis, in addition to the standard definition of who is a continuous user of a chosen method, choosers of coitally-dependent methods will also be categorized as continuous users if they:

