 - Continuation of the chosen method four months after enrollment, without a gap of four consecutive weeks or more. In order to be considered continuous users. If participants completed a 4-month follow-up survey, they must have started their chosen method by the date that survey to be considered continuous users. If they did not complete a 4-month follow-up survey and only

completed a 7-month follow-up survey, they must have started their chosen method by 20 weeks post-enrollment (4 weeks after 4-month follow-up milestone). Participants must be currently using their chosen method at the time of the 4-month follow-up survey to be considered continuous users, UNLESS they report this non-use as part of a <4week gap at the time of the 7-month survey.

- *Definition of continuation variable:* We will evaluate continuation based on the day of 4-month survey completion, within a 4-week window beginning 4 months after enrollment
- *Definition of chosen method:* For primary analysis, we will collapse IUD types for chosen method; we will conduct an additional sensitivity analysis in which we do not collapse IUD types
- *Treatment of bridge method users:* For primary analysis, any combination of continuous bridge method use with or without subsequent use of the chosen method will be considered continuous; we will conduct a sensitivity analysis in which participants who never start their primary OR start their primary method after 4mo follow-up survey are not considered continuous users of their chosen method
- *Treatment of women who become pregnant.* Continuation at 4 months will be multiply imputed for participants reporting a pregnancy before this point who had started their method and continued to use it until they became pregnant and for those who never started their method before their 4 month survey. Participants reporting starting and then discontinuing their chosen method prior to pregnancy will be counted as non-continuers.
- *Continuous users of coitally-dependent methods:* For primary analysis, in addition to the standard definition of who is a continuous user of a chosen method, choosers of coitally-dependent methods will also be categorized as continuous users if they:
 - 1) Did not have a gap of 4+ weeks during which they were sexually active and did not use a Tier 1 or Tier 2 method at any point since enrollment for four weeks or more (asked about a gap when were sexually active in the gap question) OR

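### The deadline for starting the chosen method depends on which survey a woman returned and when, and the 4-month outcome imputes pregnant women known never to have started

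*SAP*

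**What the plan says.** **Start deadline.** The SAP (Outcomes of Interest, Primary outcome) has two rules. If a woman completed the 4-month survey, "they must have started their chosen method by the date of that survey to be considered continuous users". If she completed only the 7-month survey, "they must have started their chosen method by 20 weeks post-enrollment (4 weeks after their 4-month follow-up milestone"). The 4-month continuation outcome, listed under Secondary outcomes, repeats both rules.

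**Survey window.** Protocol III.B.1 (Patient Follow-Up Survey) says "4 month follow up calls will begin at 112 days (16 weeks") and "Contact attempts for the 4- and 7-month follow-up surveys will be declared unsuccessful after 4 weeks". For the 4-month outcome the SAP says "We will evaluate continuation based on the day of 4-month survey completion, within a 4-week window beginning 4 months after enrollment".

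**Current use.** At both time points a 4-month responder must also be using the method on her survey day. The 4-month outcome words the exception as "UNLESS they report this non-use as part of a <4week gap at the time of the 7-month survey". Under Methods of Analysis, a woman who is negative at her 4-month survey "will be considered negative for the primary outcome at 7 months, regardless of whether they completed a 7-month survey or not".

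**Pregnancy.** At 7 months the SAP imputes only women who had started before 4 months and were still using the method when they conceived. Those who stopped before pregnancy are non-continuers, and never-starters are not mentioned. At 4 months the SAP imputes women who used the method until conception and also those who had not started by their 4-month survey.

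**Exceptions and safeguards.** Continuous bridge-method use counts as continuation, and coitally-dependent methods have their own rules. Ambiguous cases go to blinded adjudication under a rule list that the documents do not reproduce. Record review covers, among others, "participants who were not reached to complete a 4-month survey, but did complete a 7-month survey".

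**The concern.** Continuation should be a fact about method use. Under these rules it also depends on whether, and on what day, a woman answered the 4-month survey. Suppose two women both start on day 125. The one who answered on day 115 is a fixed failure, while the one who missed that survey can be a success. If response or its timing differed by arm, part of the estimated effect would reflect survey behaviour.

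The 4-month pregnancy rule is a separate inconsistency. It treats a known fact, that she never started, as a missing value, and it allows the imputation model to call her a continuer. This conflicts with the start rule in the same 4-month definition and with the handling at 7 months.

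**Working it through.** **1. The plan's own figure.** 112 days / 7 = 16 weeks, and 16 + 4 = 20 weeks (day 140). The 20-week deadline is therefore the end of the 4-month contact window, and the SAP's figure reproduces exactly. A responder's deadline is her survey day, which can be up to 4 weeks earlier.

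**2. One history under each response pattern.** Take a woman who starts in week 18 and then uses the method continuously. She has no bridge method, is not pregnant, and her method is not coitally dependent.

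| Surveys returned | Primary outcome as written | With a common week-16 deadline |
|---|---|---|
| 4-month at week 16, with or without 7-month | non-continuer | non-continuer |
| 4-month at week 19, and 7-month | continuer | non-continuer |
| 4-month at week 19 only | imputed | non-continuer |
| 7-month only | continuer | non-continuer |
| neither | imputed | imputed |

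A week-16 deadline gives one code wherever a start date is known. A common week-20 deadline would not: in the first row she was not using the method on her survey day, so she still fails the separate current-use test.

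**3. Number affected.** From Protocol VII.B (Sample Size): N = 758, 20% loss, continuation 50-62%. Assumptions: 80% answer each survey, independently; a share u = 1-3% start in weeks 16 to 20; answers are spread evenly over the window, so half of these starters answer after starting; a proportion r = 0.50-0.62 otherwise succeed.

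- 4-month responders: 758 x 0.8 = 606.
- Successes that a week-16 deadline turns into failures: [606 x u x 0.5 + 758 x 0.2 x u] x 0.8 x r.
- Low end: (3.03 + 1.52) x 0.8 x 0.50 = 1.8. High end: (9.09 + 4.55) x 0.8 x 0.62 = 6.8.
- In addition, late starters who answered at 4 months after starting and were lost at 7 months move from imputed to failure: 606 x u x 0.5 x 0.2 = 0.6 to 1.8.

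**4. Possible bias.** If one arm answers a week later in the 4-week window, the false difference is u x 0.25 x r x 0.8. This is 0.01 x 0.25 x 0.50 x 0.8 = 0.10 points, up to 0.03 x 0.25 x 0.62 x 0.8 = 0.37 points. With equal timing and response it is zero.

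**5. Pregnant never-starters.** The sample-size table gives 5% unintended pregnancy. Assume half occur by 4 months, 80% respond, and 25-50% of these women had never started. Then 0.05 x 758 x 0.5 x 0.8 x (0.25 to 0.50) = 3.8 to 7.6 women, or 0.6-1.3% of 606 outcomes. Only the 4-month secondary outcome is affected.

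**6. Short gap at 4 months, then lost.** Such a woman is coded a failure, because only the 7-month survey can excuse her. If s = 1-3% are in a short gap, 758 x 0.8 x 0.2 x s = 1.2 to 3.6 women. The survey cannot separate them from women who have recently stopped for good. If discontinuation (38-50%) is spread evenly over 31 weeks, stops in the last 4 weeks are 0.38 x 4/31 = 4.9% to 0.50 x 4/31 = 6.45%. The share of this combined group who truly fail is (stops + s(1 - r)) / (stops + s). The low end is (4.9 + 3 x 0.38) / 7.9 = 76% and the high end is (6.45 + 1 x 0.50) / 7.45 = 93%. Failure is usually the right code.

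**The case against.** The rules are disclosed and apply alike in both arms. Assessing a woman on the day she answers is a natural choice, and the end of the contact window is a reasonable stand-in when there is no such day. That stands as a defence of the primary definition, which need not change. It does not make the two deadlines equal.

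Adjudication and record review might absorb these cases. The rule list is not available to check, however, and nothing written equalises the deadlines, so a reviewer would apply the same unequal rule.

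Imputing women who conceived before starting could be deliberate, with pregnancy treated as an interrupting event. The SAP gives no such reason and does not do it at 7 months. Non-continuer status at 7 months is, however, an inference from the general start rule, because the pregnancy bullet does not name never-starters.

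Two stronger readings are tempting, and the documents support neither:

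- A reader might infer that a common week-20 deadline would rescue women who answered early and started later. The current-use test still fails them.
- A reader might infer that the carry-forward contradicts the short-gap exception. It does not: the 4-month definition contains the same exception, so a woman it excuses is not negative at 4 months. Record review of women who stopped before the 4-month survey and restarted before the 7-month survey points the same way. Coding a woman as a failure when she reports non-use and is then lost is a defensible convention.

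**Conclusion.** The point holds and is minor. The start deadline varies with survey return and timing at both time points, and the 4-month pregnancy rule conflicts with its own start rule and with the 7-month handling. The short-gap case needs at most one clarifying sentence.

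The sizes rest on assumed shares, since the documents give no counts of late starters or pregnant never-starters. On those assumptions, about 2-7 primary outcomes would move from success to failure under a common week-16 deadline, and about 4-8 women would be imputed at 4 months although known not to have started.

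A reader might infer that the treatment comparison is biased. The documents do not support that. Bias needs response, or its timing, to differ by arm. Nothing suggests that it does, and Protocol III.B.3 (Blinding) says phone interviewers were not told the arm. Even a one-week shift gives at most about 0.4 points against the 12-point target. The informative-missingness analyses ([MD-5]) do not examine this, because they vary only outcomes coded missing.

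**What to change.** 1. Remove the never-started clause from the 4-month pregnancy rule. State that pregnant never-starters not covered by the bridge or coitally-dependent rules are non-continuers at both time points. The SAP's coitally-dependent bullets already note that no participants met two of the criteria, so some outcome data had been seen. The 4-month result should therefore also be reported under the rule as now written.
2. Keep the primary definition and add one sensitivity analysis, derived blind to arm, with a common week-16 start deadline for all women whichever survey they returned. Women without a start date keep their current code and are counted. Report the number of outcomes changed, by arm, including those that move from imputed to failure.
3. Add a sentence to Methods of Analysis saying that the short-gap exception is applied before the carry-forward. An analysis that imputes short-gap women lost at 7 months is optional. If run, it should be limited to women who had started and recently stopped.

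The cost is two wording changes, a few recoded 4-month secondary outcomes and one extra analysis on data already held.
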